10.1 Disposition of Subjects

Figure 2: CONSORT Flow Diagram

[Implementation Note: CONSORT flow diagram will show numbers of subjects screened and enrolled. By Dose Group it will also display the number randomized, treated, and completed the study. Additionally, the diagram will show the number of subjects excluded from analysis populations by reason for exclusion.]

Placeholder for Figure 2 – CONSORT Flow Diagram

14.3.1.2 Unsolicited Adverse Events

Figure 3: Proportion of Subjects with Related Adverse Events by MedDRA SOC and Maximum Severity – All Dose Groups

[Implementation Note: This figure includes serious and non-serious unsolicited adverse events related to the study product. Note that this figure will present the number of subjects with each type of SOC. A subject will only be counted once for the same SOC for the maximum severity reported. Each figure panel will show counts for all SOCs observed in the Any Dose Group during the study (as a related AE). If the number of SOCs is too large to fit using 2 rows of panels, then the figure can be split with one row of 3 panels in each figure.]

Subjects who received VT-1598 in both Cohorts 3 and 6 will be summarized separately for each dose received in the Any Dose Group. Similarly, subjects who received placebo in both Cohorts 3 and 6 will be summarized separately for each dose received in the Placebo Dose Group.

Order SOCs alphabetically.]

[figure not shown]
[figure not shown]

Figure 4: Number of Related Adverse Events by MedDRA SOC and Severity – All Dose Groups

[Implementation Note: This figure includes serious and non-serious unsolicited adverse events related to the study product. Note that this figure will present the total counts of adverse events, a subject may contribute more than one count for the same type of adverse event. Each figure panel will show counts for all SOCs observed in any Dose Group during the study (as a related AE). If the number of SOCs is too large to fit using 2 rows of panels, then the figure can be split with one row of 3 panels in each figure.]

Subjects who received VT-1598 in both Cohorts 3 and 6 will be included separately for each dose received in the Any Dose Group. Similarly, subjects who received placebo in both Cohorts 3 and 6 will be included separately for each dose received in the Placebo Dose Group.

Order SOCs alphabetically.]

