3.3.2. Dose Group

Dose Group defines a grouping of subjects for statistical analysis, where subjects within a Dose Group receive the same study product and dose under the same fasting status. Two combined Dose Groups, the Any Dose and Placebo Dose Groups, will include all subjects who receive the same study product (VT-1598 or Placebo, respectively) regardless of the subject's fasting status. Subjects who participate in both Cohort 3 and Cohort 6 will be counted separately for each dosing period based on the study product received. Any summary tables including a column for 'All Subjects' will also count Cohort 3 and Cohort 6 subjects separately for each dosing period. For data from a subject to be analyzed as part of their Dose Group, the subject must also qualify for inclusion into the respective analysis population (Section 6.3). The Dose Groups in the order they will be presented are defined as follows:

- Any Dose: All subjects who received a complete or incomplete dose of VT-1598 regardless of fasting status. Subjects who received VT-1598 in Cohort 3 and continued to Cohort 6 will be included in the Any Dose Group separately for each dosing period.
- 40 mg Fasted: Cohort 1 subjects who received a complete dose of active drug under a fasted state.
- 80 mg Fasted: Cohort 2 subjects who received a complete dose of active drug under a fasted state.
- 160 mg Fasted: Cohort 3 subjects who received a complete dose of active drug under a fasted state.
- 160 mg Fed: Cohort 6 subjects who received a complete dose of active drug following a high-fat, high-calorie meal.
- 320 mg Fasted: Cohort 4 subjects who received a complete dose of active drug under a fasted state.
- 640 mg Fasted: Cohort 5 subjects who received a complete dose of active drug under a fasted state.
- Placebo: All subjects who received a complete or incomplete dose of placebo, regardless of fasting status. Subjects who received placebo in Cohort 3 and continued to Cohort 6 will be included in the Placebo group separately for each dosing period (unless replaced as detailed in Section 4.4.3).

Analyses by Dose Groups will be presented in the following order: Any Dose (when included), 40 mg Fasted, 80 mg Fasted, 160 mg Fasted, 160 mg Fed, 320 mg Fasted, 640 mg Fasted, and Placebo.

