9.3. Adverse Events

When calculating the proportions of subjects with AEs within a given MedDRA category, subjects will be counted once for each dosing period within the same MedDRA category, and the event will be reported according to the highest severity recorded throughout the indicated time period (separately for related and unrelated AEs when both severity and relatedness are tabulated). Repeated AEs will be ignored. When calculating the number of AEs that occurred, all AEs will be summarized by Dose Group, including repetitions.

All reported adverse events will be included in the summaries and analyses.

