9.3.2. Unsolicited Adverse Events

An overall summary of unsolicited AEs by Dose Group will be presented in [Table 17](#) including the number of subjects with at least one AE, number of subjects with at least one related AE, and number of subjects with at least one SAE.

All AEs will be presented in [Listing 11](#). A subject listing of non-serious AEs of moderate or greater severity will also be reported ([Table 22](#)).

Denominators for proportions are the number of subjects in the Safety Population in each Dose Group. Placebo subjects who participated in both Cohort 3 and Cohort 6 will contribute to the denominator once per each dosing period for the Placebo Dose Group. Subjects who received VT-1598 and participated in both Cohort 3 and Cohort 6 will contribute to the denominator once per each dosing period for the Any Dose Group. The following summaries for unsolicited AEs will be presented:

- The number of AEs and number and proportion of subjects reporting an AE or SAE that occurred in 5% of all subjects along with the total number of events reported will be presented by Dose Group, SOC, HLTG, and preferred term (PT) ([Table 18](#)).
- The number of AEs and number and proportion of subjects reporting an AE will be presented by Dose Group, SOC, HLTG, and PT. The 95% CI for the proportion of subjects experiencing each SOC/HLTG/PT will also be presented ([Table 19](#)).
- The number and proportion of subjects reporting a related or unrelated AE will be presented by Dose Group, SOC, HLTG, PT, severity, and relationship to study product. ([Table 20](#))

Summaries of unsolicited AEs will be presented graphically in bar charts by Dose Group and SOC. For summaries of proportions of subjects reporting an AE, denominators will be the number of subjects in the Safety Population for each Dose Group. Placebo subjects who participated in both Cohort 3 and Cohort 6 will

contribute to the denominator once per each dosing period. Subjects who received VT-1598 and participated in both Cohort 3 and Cohort 6 will contribute to the denominator once per each dosing period for the Any Dose Group:

- The proportion of subjects reporting a related AE will be presented by the maximum severity reported per SOC ([Figure 3](#)).
- The total number of related AEs reported will be presented by Dose Group and SOC ([Figure 4](#)).

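### The SAP Figure 3 note picks its system organ classes from VT-1598 recipients alone, so related AEs in a class seen only on placebo would be missing from the figure; it also asks for counts where the SAP text specifies proportions

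*SAP*

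**What the plan says.** Two figure shells sit side by side in SAP Appendix 2, under 14.3.1.2 Unsolicited Adverse Events.

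- **Figure 3, SOC list:** "Each figure panel will show counts for all SOCs observed in the Any Dose Group during the study (as a related AE".
- **Figure 4, SOC list:** "Each figure panel will show counts for all SOCs observed in any Dose Group during the study (as a related AE".
- **Figure 3, quantity shown:** "Note that this figure will present the number of subjects with each type of SOC". The figure's own title, however, calls for a proportion of subjects.
- **SAP 9.3.2, for Figure 3:** "The proportion of subjects reporting a related AE will be presented by the maximum severity reported per SOC". The denominator given there is the Safety Population of each Dose Group.

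SAP 3.3.2 supplies the two group definitions that matter: "Any Dose: All subjects who received a complete or incomplete dose of VT-1598 regardless of fasting status" and "Placebo: All subjects who received a complete or incomplete dose of placebo, regardless of fasting status". Placebo is therefore a separate combined group and no part of Any Dose. It is nevertheless meant to appear in Figure 3, because the note says that "subjects who received placebo in both Cohorts 3 and 6 will be summarized separately for each dose received in the Placebo Dose Group".

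**The concern.** The SOCs to be displayed are chosen from the outcomes of one arm and then applied to both. An SOC with a related event only on VT-1598 is always shown. One with a related event only on placebo is never shown, not even in the Placebo panel. The filter can remove placebo events but never VT-1598 events.

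Safety is the primary objective, and SAP 4.2 names pooled placebo as the comparator. Figure 3 is the planned graph of subject-level proportions for related events; Figure 4 shows event totals. A reader of Figure 3 could take an absent class to mean that no related event occurred there in any group.

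The second issue is the quantity plotted. The groups differ in planned size by a factor of up to six, so counts cannot be compared by eye across panels. The note's wording and the SAP text cannot both be programmed.

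**Working it through.** **Step 1. Compare the texts.**

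| Item | Figure 3 note | Figure 4 note | SAP body and figure title |
|---|---|---|---|
| Source of SOC list | Any Dose Group (VT-1598 only, by SAP 3.3.2) | Any of the Dose Groups, so Placebo is included | No SOC restriction stated in 9.3.2 |
| Quantity | Number of subjects; counts | Event counts (as intended for Figure 4) | Figure 3: proportion over Safety Population N |

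The term in the Figure 3 note is the defined one. The same note uses it again for VT-1598 recipients and sets it against the Placebo Dose Group. A programmer following the note would filter on VT-1598.

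**Step 2. Planned group sizes.** Each of six cohorts has 6 VT-1598 and 2 placebo subjects (SAP 2; Protocol 3.1.3), and subjects in both Cohorts 3 and 6 count once per dosing period (SAP 3.3.2).

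- Any Dose: 6 × 6 = 36
- Placebo: 6 × 2 = 12
- Each active dose group: 6
- Total: 36 + 12 = 48, which agrees with the planned 48.

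**Step 3. How often an SOC would be dropped.** The documents give no related-AE rate. Assume one rate p per SOC, equal in both arms, with independent dosing periods.

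- Placebo has at least one: 1 − (1 − p)^12
- VT-1598 has none: (1 − p)^36. This is also the chance of omission given that placebo has an event.
- SOC dropped: the product of the two
- Expected placebo subjects omitted per SOC: 12p(1 − p)^36

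| p | Placebo ≥ 1 | VT-1598 none | SOC dropped | Expected placebo subjects omitted |
|---|---|---|---|---|
| 1% | 0.114 | 0.696 | 0.079 | 0.08 |
| 2% | 0.215 | 0.483 | 0.104 | 0.12 |
| 3% | 0.306 | 0.334 | 0.102 | 0.12 |
| 5% | 0.460 | 0.158 | 0.073 | 0.09 |
| 10% | 0.718 | 0.023 | 0.016 | 0.03 |

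The last column peaks at p = 1/37: (12/37) × (36/37)^36 ≈ 0.12. When an SOC is dropped, the mean number of placebo subjects lost is 12p divided by the second column: 0.24/0.215 ≈ 1.1 at 2% and 0.60/0.460 ≈ 1.3 at 5%.

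Across several SOCs the chance accumulates. For p of 1%, 2% and 5%, the probability that at least one SOC is dropped is 34%, 42% and 31% with 5 independent SOCs, and 56%, 67% and 53% with 10. The numbers of SOCs are also assumptions.

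With the Figure 4 rule, every SOC with a placebo related event is listed, so the omission probability is 0.

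**Step 4. Counts against proportions.** Two affected subjects are 2/6 = 33% in an active dose group, 2/12 = 17% in Placebo and 2/36 = 6% in Any Dose. As counts, the three bars have the same height. Conversely, equal true rates give expected counts in the ratio 6 : 12 : 36.

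**The case against.** The strongest reply is that this is a drafting slip. The Figure 3 and Figure 4 sentences are otherwise identical, Figure 3 is titled for all Dose Groups, and its note says how placebo is to be counted. Nothing states an intention to select on active-arm outcomes, and the note does not contain the word *only*. That is plausible, but the words as they stand name a defined group and would be programmed that way.

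On counts, SAP 9.3.2 and the title both say proportion, and they would probably prevail. The mock-up image is not available, so the axis cannot be checked, nor whether N is already printed. What stands is an inconsistency in the note, not proof that counts would be plotted.

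No data are lost. Table 20 gives number and percentage by SOC, severity and relationship, with Placebo included. Table 17, Table 19, Figure 4 and Listing 11 also carry placebo events. The primary analyses are descriptive (SAP 6.8), so no inference depends on this figure, and the distortion cannot hide a VT-1598 signal. All of this stands, and it keeps the point minor.

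Three stronger readings are tempting, and the documents do not support them.

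- *Placebo is understated wherever it did worse.* With 3 of 12 on placebo and 1 of 36 on VT-1598, placebo is worse and the SOC is still shown in full. Only SOCs with no VT-1598 related event are dropped.
- *The note breaches SAP 9.3*, which says: "All reported adverse events will be included in the summaries and analyses". Individual displays are restricted by design: Figure 3 to related events, Table 18 to a 5% threshold.
- *Figure 3 would contradict Table 20.* The SOC rule removes rows; it changes no value that is displayed.

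**Conclusion.** The point holds as a minor defect in one figure shell. As written, the Figure 3 note omits from every panel any SOC whose related events occurred on placebo alone, and its wording on the plotted quantity conflicts with the figure's title and SAP 9.3.2.

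The effect is conditional on such an SOC occurring and is confined to this display. Typically it would be one missing bar for a single placebo subject. Its direction is to make VT-1598 look relatively worse.

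The sizes rest on planned numbers, an equal rate in both arms and independent dosing periods; none of the rates comes from the documents. Independence across dosing periods is a mild assumption, since SAP 15 reports that only one subject from the fasted 160 mg cohort returned for the fed cohort.

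**What to change.** In the Figure 3 implementation note:

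1. Take the SOC list from any Dose Group, including Placebo, as the Figure 4 note does.
2. Replace the references to numbers of subjects and counts with the proportion of subjects over each Dose Group's Safety Population N, to agree with the title and SAP 9.3.2. Show N in each panel if the mock-up does not already do so.

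The cost is a rewording of one shell. The figure may gain a few SOC rows, and the note already allows it to be split. No new data or analyses are needed.

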14.3.5 Displays of Laboratory Results

14.3.5.1 Chemistry Results

Figure 5: Chemistry Laboratory Results by Scheduled Visits: Change from Baseline by Parameter, Dose Group, and Timepoint – Albumin

[Implementation Note: Subjects who received VT-1598 in both Cohorts 3 and 6 will be included separately for each dose received in the Any Dose Group. Similarly, subjects who received placebo in both Cohorts 3 and 6 will be included separately for each dose received in the Placebo Dose Group.]

[figure not shown]

Figure 6: Chemistry Laboratory Results by Scheduled Visits: Change from Baseline by Parameter, Dose Group, and Timepoint – Glucose

This figure will repeat Figure 5 for Glucose

Figure 7: Chemistry Laboratory Results by Scheduled Visits: Change from Baseline by Parameter, Dose Group, and Timepoint – Blood Urea Nitrogen

This figure will repeat Figure 5 for Blood Urea Nitrogen

Figure 8: Chemistry Laboratory Results by Scheduled Visits: Change from Baseline by Parameter, Dose Group, and Timepoint – Potassium

This figure will repeat Figure 5 for Potassium

Figure 9: Chemistry Laboratory Results by Scheduled Visits: Change from Baseline by Parameter, Dose Group, and Timepoint – Calcium

This figure will repeat Figure 5 for Calcium

Figure 10: Chemistry Laboratory Results by Scheduled Visits: Change from Baseline by Parameter, Dose Group, and Timepoint – Sodium

This figure will repeat Figure 5 for Sodium

Figure 11: Chemistry Laboratory Results by Scheduled Visits: Change from Baseline by Parameter, Dose Group, and Timepoint – Chloride

This figure will repeat Figure 5 for Chloride

Figure 12: Chemistry Laboratory Results by Scheduled Visits: Change from Baseline by Parameter, Dose Group, and Timepoint – Total Protein

This figure will repeat Figure 5 for Total Protein

Figure 13: Chemistry Laboratory Results by Scheduled Visits: Change from Baseline by Parameter, Dose Group, and Timepoint – Creatinine

This figure will repeat Figure 5 for Creatinine

Figure 14: Chemistry Laboratory Results by Scheduled Visits: Change from Baseline by Parameter, Dose Group, and Timepoint – Triglycerides

This figure will repeat Figure 5 for Triglycerides

Figure 15: Chemistry Laboratory Results by Scheduled Visits: Change from Baseline by Parameter, Dose Group, and Timepoint – Total Cholesterol

This figure will repeat Figure 5 for Total Cholesterol

Figure 16: Chemistry Laboratory Results by Scheduled Visits: Change from Baseline by Parameter, Dose Group, and Timepoint – Low-Density Lipoprotein

This figure will repeat Figure 5 for Low-Density Lipoprotein

Figure 17: Chemistry Laboratory Results by Scheduled Visits: Change from Baseline by Parameter, Dose Group, and Timepoint – High-Density Lipoprotein

This figure will repeat Figure 5 for High-Density Lipoprotein

Figure 18: Chemistry Laboratory Results by Scheduled Visits: Change from Baseline by Parameter, Dose Group, and Timepoint – Total Carbon Dioxide

This figure will repeat Figure 5 for Total Carbon Dioxide

Figure 19: Chemistry Laboratory Results by Scheduled Visits: Change from Baseline by Parameter, Dose Group, and Timepoint – Creatine Phosphokinase

This figure will repeat Figure 5 for Creatine Phosphokinase

Figure 20: Chemistry Laboratory Results by Scheduled Visits: Change from Baseline by Parameter, Dose Group, and Timepoint – Phosphorus

This figure will repeat Figure 5 for Phosphorus

Figure 21: Chemistry Laboratory Results by Scheduled Visits: Change from Baseline by Parameter, Dose Group, and Timepoint – Alkaline Phosphatase

This figure will repeat Figure 5 for Alkaline Phosphatase

Figure 22: Chemistry Laboratory Results by Scheduled Visits: Change from Baseline by Parameter, Dose Group, and Timepoint – Aspartate Aminotransferase

This figure will repeat Figure 5 for Aspartate Aminotransferase

Figure 23: Chemistry Laboratory Results by Scheduled Visits: Change from Baseline by Parameter, Dose Group, and Timepoint – Alanine Aminotransferase

This figure will repeat Figure 5 for Alanine Aminotransferase

Figure 24: Chemistry Laboratory Results by Scheduled Visits: Change from Baseline by Parameter, Dose Group, and Timepoint – Total Bilirubin

This figure will repeat Figure 5 for Total Bilirubin

Figure 25: Chemistry Laboratory Results by Scheduled Visits: Change from Baseline by Parameter, Dose Group, and Timepoint – Direct Bilirubin

This figure will repeat Figure 5 for Direct Bilirubin

Figure 26: Chemistry Laboratory Results by Scheduled Visits: Change from Baseline by Parameter, Dose Group, and Timepoint – Magnesium

This figure will repeat Figure 5 for Magnesium

Figure 27: Chemistry Laboratory Results by Scheduled Visits: Change from Baseline by Parameter, Dose Group, and Timepoint – Gamma-Glutamyl Transferase

This figure will repeat Figure 5 for Gamma-Glutamyl Transferase

Figure 28: Chemistry Laboratory Results by Scheduled Visits: Change from Baseline by Parameter, Dose Group, and Timepoint – Serum Cortisol

This figure will repeat Figure 5 for Serum Cortisol

14.3.5.2 Hematology Results

Figure 29: Hematology Laboratory Results by Scheduled Visits: Change from Baseline by Parameter, Dose Group, and Timepoint – Hemoglobin

This figure will repeat Figure 5 for Hemoglobin

Figure 30: Hematology Laboratory Results by Scheduled Visits: Change from Baseline by Parameter, Dose Group, and Timepoint – Hematocrit

This figure will repeat Figure 5 for Hematocrit

Figure 31: Hematology Laboratory Results by Scheduled Visits: Change from Baseline by Parameter, Dose Group, and Timepoint – Lymphocytes

This figure will repeat Figure 5 for Lymphocytes

Figure 32: Hematology Laboratory Results by Scheduled Visits: Change from Baseline by Parameter, Dose Group, and Timepoint – Neutrophils

This figure will repeat Figure 5 for Neutrophils

Figure 33: Hematology Laboratory Results by Scheduled Visits: Change from Baseline by Parameter, Dose Group, and Timepoint – Monocytes

This figure will repeat Figure 5 for Monocytes

Figure 34: Hematology Laboratory Results by Scheduled Visits: Change from Baseline by Parameter, Dose Group, and Timepoint – Eosinophils

This figure will repeat Figure 5 for Eosinophils

Figure 35: Hematology Laboratory Results by Scheduled Visits: Change from Baseline by Parameter, Dose Group, and Timepoint – Basophils

This figure will repeat Figure 5 for Basophils

Figure 36: Hematology Laboratory Results by Scheduled Visits: Change from Baseline by Parameter, Dose Group, and Timepoint – Platelet Count

This figure will repeat Figure 5 for Platelets

Figure 37: Hematology Laboratory Results by Scheduled Visits: Change from Baseline by Parameter, Dose Group, and Timepoint – Red Blood Cell Count

This figure will repeat Figure 5 for Red Blood Cell Count

Figure 38: Hematology Laboratory Results by Scheduled Visits: Change from Baseline by Parameter, Dose Group, and Timepoint – White Blood Cell Count

This figure will repeat Figure 5 for White Blood Cell Count

14.3.5.3 Coagulation Results

Figure 39: Coagulation Laboratory Results by Scheduled Visits: Change from Baseline by Parameter, Dose Group, and Timepoint – Activated Partial Thromboplastin Time

This figure will repeat Figure 5 for Activated Partial Thromboplastin Time

Figure 40: Coagulation Laboratory Results by Scheduled Visits: Change from Baseline by Parameter, Dose Group, and Timepoint – Prothrombin Time

This figure will repeat Figure 5 for Prothrombin Time

Figure 41: Coagulation Laboratory Results by Scheduled Visits: Change from Baseline by Parameter, Dose Group, and Timepoint – International Normalized Ratio

This figure will repeat Figure 5 for International Normalized Ratio

14.3.5.4 Urinalysis Results

Figure 42: Urinalysis Laboratory Results by Scheduled Visits: Change from Baseline by Parameter, Dose Group, and Timepoint – Specific Gravity

This figure will repeat Figure 5 for Specific Gravity

Figure 43: Urinalysis Laboratory Results by Scheduled Visits: Change from Baseline by Parameter, Dose Group, and Timepoint – pH

This figure will repeat Figure 5 for pH

14.3.5.6 Displays of Vital Signs

Figure 44: Vital Signs by Scheduled Visits: Change from Baseline by Parameter and Timepoint, 40 mg Fasted, 80 mg Fasted, and 320 mg Fasted Dose Groups– Systolic Blood Pressure

[Implementation note: the presented order of dose groups in this figure contradicts the specified order of section 3.3.2 due to constraints on the number of graphs that can be presented per page. The 160 mg Fasted and Fed and the Any Dose/Placebo graphs are kept together for ease of viewing.]

[figure not shown]

Figure 45: Vital Signs by Scheduled Visits: Change from Baseline by Parameter and Timepoint, 160 mg Fasted, 160 mg Fed, and 640 mg Fasted Dose Groups– Systolic Blood Pressure

[Implementation note: the presented order of dose groups in this figure contradicts the specified order of section 3.3.2 due to constraints on the number of graphs that can be presented per page. The 160 mg Fasted and Fed and the Any Dose/Placebo graphs are kept together for ease of viewing.]

[figure not shown]

Figure 46: Vital Signs by Scheduled Visits: Change from Baseline by Parameter and Timepoint, Any Dose and Placebo Dose Groups– Systolic Blood Pressure

[Implementation Note: Subjects who received VT-1598 in both Cohorts 3 and 6 will be included separately for each dose received in the Any Dose Group. Similarly, subjects who received placebo in both Cohorts 3 and 6 will be included separately for each dose received in the Placebo Dose Group. The presented order of dose groups in this figure contradicts the specified order of section 3.3.2 due to constraints on the number of graphs that can be presented per page. The 160 mg Fasted and Fed and the Any Dose/Placebo graphs are kept together for ease of viewing.]

[figure not shown]

Figure 47: Vital Signs by Scheduled Visits: Change from Baseline by Parameter and Timepoint, 40 mg Fasted, 80 mg Fasted, and 320 mg Fasted Dose Groups– Diastolic Blood Pressure

This figure will repeat Figure 43 for Diastolic Blood Pressure

Figure 48: Vital Signs by Scheduled Visits: Change from Baseline by Parameter and Timepoint, 160 mg Fasted, 160 mg Fed, and 640 mg Fasted Dose Groups– Diastolic Blood Pressure

This figure will repeat Figure 44 for Diastolic Blood Pressure in 160 mg Fasted, 160 mg Fed, and 640 mg Fasted Dose Groups

Figure 49: Vital Signs by Scheduled Visits: Change from Baseline by Parameter and Timepoint, Any Dose and Placebo Dose Groups– Diastolic Blood Pressure

This figure will repeat Figure 45 for Diastolic Blood Pressure in the Any Dose Group and Placebo Dose Group

Figure 50: Vital Signs by Scheduled Visits: Change from Baseline by Parameter and Timepoint, 40 mg Fasted, 80 mg Fasted, and 320 mg Fasted Dose Groups– Pulse

This figure will repeat Figure 43 for Pulse

Figure 51: Vital Signs by Scheduled Visits: Change from Baseline by Parameter and Timepoint, 160 mg Fasted, SAD 160 mg Fed, and 640 mg Fasted Dose Groups – Pulse

This figure will repeat Figure 44 for Pulse in 160 mg Fasted, 160 mg Fed, and 640 mg Fasted Dose Groups

Figure 52: Vital Signs by Scheduled Visits: Change from Baseline by Parameter and Timepoint, Any Dose and Placebo Dose Groups– Pulse

This figure will repeat Figure 45 for Pulse in the Any Dose Group and Placebo Dose Group

Figure 53: Vital Signs by Scheduled Visits: Change from Baseline by Parameter and Timepoint, 40 mg Fasted, 80 mg Fasted, and 320 mg Fasted Dose Groups– Respiratory Rate

This figure will repeat Figure 43 for Respiratory Rate

Figure 54: Vital Signs by Scheduled Visits: Change from Baseline by Parameter and Timepoint, 160 mg Fasted, 160 mg Fed, and 640 mg Fasted Dose Groups – Respiratory Rate

This figure will repeat Figure 44 for Respiratory Rate in 160 mg Fasted, 160 mg Fed, and 640 mg Fasted Dose Groups

Figure 55: Vital Signs by Scheduled Visits: Change from Baseline by Parameter and Timepoint, Any Dose and Placebo Dose Groups – Respiratory Rate

This figure will repeat Figure 45 for Respiratory Rate in the Any Dose Group and Placebo Dose Group

Figure 56: Vital Signs by Scheduled Visits: Change from Baseline by Parameter and Timepoint, 40 mg Fasted, 80 mg Fasted, and 320 mg Fasted Dose Groups – Temperature

This figure will repeat Figure 43 for Temperature

Figure 57: Vital Signs by Scheduled Visits: Change from Baseline by Parameter and Timepoint, 160 mg Fasted, 160 mg Fed, and 640 mg Fasted Dose Groups – Temperature

This figure will repeat Figure 44 for Temperature in 160 mg Fasted, 160 mg Fed, and 640 mg Fasted Dose Groups

Figure 58: Vital Signs by Scheduled Visits: Change from Baseline by Parameter and Timepoint, Any Dose and Placebo Dose Groups – Temperature

This figure will repeat Figure 45 for Temperature in the Any Dose Group and Placebo Dose Group

